#### **8.4.2. Procedure for the US**

At the time of the primary analysis, no formal testing will be conducted on the endpoint of eGFR rate of change over 6 to 58 weeks. Analysis of key secondary endpoints will proceed as follows at the final analysis:

1. The key secondary endpoint of eGFR rate of change over 110 weeks following initiation of randomized therapy will be tested at a significance level of  $\alpha = 0.05$ .
2. If significant at Step 1, eGFR rate of change over 6 to 110 weeks will be tested at a significance level of  $\alpha = 0.05$ .

If at Step 1, the statistical comparison of treatment group is not statistically significant at the specified significance level, then the remaining comparisons will be considered descriptive and exploratory.

[figure not shown]
#### **8.4.3. Procedure for Testing Other Secondary Endpoints Within the US and Non-US Countries**

At the time of the final (confirmatory) analysis, if all the key secondary endpoints achieve statistical significance within the US or non-US countries, the other secondary endpoints will be statistically tested at the available alpha in the order specified below:

1. The mean change from baseline in UP/C at Week 110
2. The mean change from baseline in urine protein excretion at Week 110
3. The mean change from baseline in UA/C at Week 110
4. The mean change from baseline in urine albumin excretion at Week 110
5. The proportion of patients reaching a confirmed 40% reduction in eGFR, ESRD, or death
6. The mean change from baseline in eGFR at Week 110

The multiple testing strategies for the US and for non-US countries are shown in [Figure 1](#).

**Figure 1: Multiple Testing Strategies for US and Non-US Countries**

eGFR = estimated glomerular filtration rate; US=United States.

## 8.5. Analysis of the Primary Efficacy Endpoint

### 8.5.1. Primary Efficacy Analysis

The primary efficacy analysis will be based on the PAS (at primary analysis) and FAS (at final analysis) and change from baseline (Day 1) in proteinuria (UP/C) will be analyzed via an MMRM analysis. The dependent variable will be UP/C change from baseline. As UP/C is a highly right-skewed variable, analyses will be performed on log-transformed data. The model will include the following fixed effects:

- Treatment group (2 levels: sparsentan, irbesartan)
- Baseline UP/C in log scale
- Time (ie, analysis visit in weeks)
- Treatment group by time interaction
- Randomization stratification variable (4 levels based on Screening eGFR and urine protein excretion)

In addition, patient will be included as a random effect.

Under the assumption of MAR, missing data will be imputed using the MI procedure (Ouyang 2017; Rubin 1987) for the UP/C result in the natural log scale. Specific imputation procedures are provided in [Section 6.6.1.1](#).

An unstructured covariance matrix will be used. If the computational algorithm fails to converge, the following structures will be executed: heterogeneous Toeplitz, heterogeneous Compound Symmetry, heterogeneous first-order autoregressive, Toeplitz, Compound Symmetry, and first-order autoregressive.

The treatment effect will be the contrast between sparsentan and irbesartan LS means at Week 36. The LS means, treatment effect estimate (difference in LS means), 95% CI, and 2-sided p-value will be extracted from the model. Results will be back-transformed to present treatment effects on the ratio scale.

Estimates and CIs will be converted to percentages via the following transformations:

$$[\exp(\text{LS mean change from baseline in natural log(UP/C)}) - 1] \times 100$$

### 8.5.2. Sensitivity Analyses of the Primary Efficacy Results

Robustness of the primary analysis of the primary efficacy endpoint due to missing data or premature treatment discontinuations (including the impact of COVID-19) will be explored by the following sensitivity analyses:

- Tipping point approach of the MI analysis as described in [Section 6.6.1.2](#)
- MMRM analysis using observed data (with no imputation of missing data)
- MMRM analysis using completers only (patients with non-missing UP/C values at Week 36 (212 to 295 days))

- MMRM analysis using observed data (with no imputation of missing data) during the double-blind period including after premature treatment discontinuation (treatment policy estimand). Additional analysis exploring potential intercurrent events that could impact the primary analysis (eg, premature discontinuation of study drug, use of immunosuppressive agents, loss to follow-up, withdrawal of consent, need for RRT, or death) may be performed to examine their impact.

To assess the impact of changes in systemic immunosuppressive medications, the primary efficacy analysis will be repeated by excluding assessments after initiation of renal indication of systemic immunosuppressive medication in the blinded treatment period.

To assess the potential impact of patient evaluability and major protocol deviations, the primary efficacy analysis will be repeated using the PP Analysis Set.

## **8.6. Analysis of the Key Secondary Efficacy Endpoints**

### **8.6.1. Rate of Change in eGFR Following Acute Effect of Randomized Therapy**

The rate of change in eGFR over 52 weeks and 104 weeks following acute effect will each be analyzed via a mixed model random coefficients analysis. The dependent variable will be eGFR measured over 52 weeks (Week 6 to Week 58) or over 104 weeks (Week 6 to Week 110). The model will include the following fixed effects:

- Treatment group (2 levels: sparsentan, irbesartan)
- Baseline eGFR
- Time (ie, analysis visit in weeks)
- Treatment group by time interaction
- Randomization stratification variable (4 levels based on Screening eGFR and urine protein excretion)

In addition, the model will also include a random intercept and random slope for each patient.

Under the assumption of MAR, missing data will be imputed using the MI procedure (Ouyang 2017, Rubin 1987). Specific imputation procedures are provided in [Section 6.6.1.1](#).

An unstructured covariance matrix will be assumed; if convergence issues arise, a first order autoregressive structure will be used.

The treatment effect will be the contrast between sparsentan and irbesartan marginal slope estimates. The associated slope estimates, difference in slopes, 95% CI, and 2-sided p-value will be extracted from the model. Slope and the difference in slopes will be annualized for ease of presentation and interpretation.

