Approximately 380 patients will be required to detect an underlying treatment effect in the rate of change in eGFR over 110 weeks following the initiation of randomized therapy (eGFR total slope at 2 years) of 2.9 mL/min/1.73 m^2 per year with 90% power. In addition, approximately 380 patients provide 80% power to detect a smaller treatment effect on eGFR slope at 2 years of 2.55 mL/min/1.73 m^2 per year. Consequently, approximately 380 patients provide more than 90% power to detect an underlying treatment effect in the rate of change in eGFR over 104 weeks following the initial acute effect of randomized therapy (eGFR chronic slope at 2 years) of 3.15 mL/min/1.73 m^2 per year. With this sample size, the observed annualized treatment difference to yield a p-value <0.02 is 1.8 mL/min/1.73 m^2 per year. These sample size and power calculations follow the method described by Dupont (Dupont 1998), with 1-sided  $\alpha = 0.02$  and residual error of 5.8 mL/min/1.73 m^2 estimated from a random coefficient analysis of the Leicester University Hospital Registry. The projected treatment effects on the rate of change in eGFR were based on a meta-analysis of clinical studies in IgAN using the methodology presented by Inker (Inker 2019).

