#### 4.4. Randomization

Randomization will be carried out using an interactive response technology (IRT) system, with central randomization following a 1:1 ratio between the 2 treatment arms, based on a permuted-block randomization method. Randomization will be stratified by the following factors:

- eGFR value at Screening (30 to <60 mL/min/1.73 m^2 and ≥60 mL/min/1.73 m^2)
- Urine protein excretion at Screening (≤1.75 g/day and >1.75 g/day)

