### 6.6.1. Missing Efficacy Endpoints – Proteinuria and eGFR Slope

#### 6.6.1.1. Primary Analysis

For the primary analysis of primary endpoint of proteinuria and key secondary efficacy endpoints of eGFR slopes, missing central laboratory data will be imputed using the multiple imputation (MI) procedure ([Ouyang 2017](#), [Rubin 1987](#)). Under the missing at random (MAR) assumption, a Bayesian multivariate normal model for the data will be fitted using a Markov Chain Monte Carlo (MCMC) approach. Quasi-independent samples will be drawn from the posterior distributions for the parameters of the multivariate normal distribution for each arm. A non-informative prior will be used. The MCMC approach allows all missing observations to be imputed, whether a patient has monotone or non-monotone pattern of missingness. Monotone missing pattern is when a data point is missing for an individual patient then all subsequent data points are missing for that patient, whereas a non-monotone missing pattern implies data points are missing in intermediate visits for a patient. The seed number for the random generator will be defined and documented before study unblinding.

Following the approach described in [Ouyang \(Ouyang 2017\)](#), the following imputation procedures will be implemented:

1. Intermittent missing values before a discontinuation event (ie, discontinuation of randomized therapy or early permanent dropout): the MAR assumption is reasonable for intermittent missing values before a discontinuation event since the values of the endpoint before and after the intermittent missing value are known. Imputation of intermittent missing data will be accomplished using the MCMC option in SAS PROC MI (SAS, 2008) by treatment group to impute intermittent missing data without a monotone missing pattern, prior to performing imputations of values following the discontinuation event.
2. Missing data following a discontinuation event (ie, discontinuation of randomized therapy or early permanent dropout): impute the post discontinuation missing data by treatment group under the assumption of MAR using the regression option from the monotone statement of SAS PROC MI. Baseline and post-baseline scheduled visits will be used in the regression option to impute the missing values.
3. Repeat Steps 1 and 2 to generate 30 multiply imputed datasets.

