## 8. EFFICACY

### 8.1. General Considerations

All efficacy analyses will be based on the FAS or PAS as described below. The primary and key secondary endpoint analyses will also be performed on the PP Analysis Set as supportive analyses. All primary efficacy analyses based on laboratory data will use central laboratory data only. All efficacy analyses specified below refer to the double-blind period only.

Proteinuria (UP/C) will be determined based on a 24-hour urine sample. As UP/C is a highly right-skewed variable, analyses will be performed on log-transformed data. For ease of interpretation, results will be presented in the original units.

The eGFR for each baseline and post-baseline visit will be determined using the Chronic Kidney Disease Epidemiology Collaboration ([Levey 2009](#)) formula for adults based on serum creatinine values from the visit.

For the purposes of efficacy analyses, an assessment is considered “on treatment” if it occurs after the first dose of study medication and no more than 3 days after the date of last dose of randomized treatment for the patient.

For all least squares (LS) means that include strata coefficients, the observed strata proportions will be used instead of assuming equal sizes of strata.

Longitudinal analyses of UP/C and eGFR (eg, via MMRM for continuous endpoints or generalized linear mixed models for binary endpoints) will consider data from post-baseline visits through Week 110 of the double-blind period. At the primary analysis, if there are issues with model converge due to sparsity of measurements at the later visits (ie, Week 106 or Week 110), then the longitudinal analyses will include only data through an earlier visit (ie, Week 94) to enable the analyses. The last visit to be included in the analyses will be appropriately documented in a note to file prior to unblinding for the primary analysis.

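### The confirmatory eGFR slope models adjust for the randomization strata only as main effects, so the slope test stays valid but is conservative if the strata predict slope (low-priority improvement)

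*SAP*

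**What the plan says.** SAP 8.6.1 (chronic slope, Weeks 6 to 58 and 6 to 110) and 8.6.2 (total slope to Week 110) specify the same model. Its fixed effects are treatment, baseline eGFR, time, treatment-by-time and the "Randomization stratification variable (4 levels based on Screening eGFR and urine protein excretion"), and each patient has a random intercept and a random slope. No stratum-by-time or baseline-by-time term is listed. The tested quantity is the difference between the arms in marginal slope. The covariance is unstructured, and "if convergence issues arise, a first order autoregressive structure will be used". SAP 8.7.1 and the spline model in 8.6.3.1 also carry the strata as a main effect only.

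Missing values are multiply imputed by treatment group (SAP 6.6.1.1): "The MCMC approach allows all missing observations to be imputed", and after discontinuation "Baseline and post-baseline scheduled visits will be used in the regression option to impute the missing values". The strata are not named as imputation predictors.

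Randomization is stratified by the same two screening factors and is "based on a permuted-block randomization method" (SAP 4.4). Protocol 12.7.2.1 and 12.7.2.2 say the slope analyses are stratified by the randomization strata, without saying in what form.

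**The concern.** In the Week 36 UP/C model (SAP 8.5.1) the tested quantity is a mean difference, so a stratum main effect adjusts it. In the slope models the same line of the specification acts on level only. The stratification then never reaches the parameter that decides the confirmatory tests.

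Stratified permuted blocks balance the strata between arms. If strata predict slope, that balance reduces the true sampling variance of the slope difference. A model without stratum-by-time leaves the between-stratum slope variation in the random-slope variance and reports the wider standard error. Confidence intervals are then too wide and p-values too large. Some precision that the design has already bought goes unused. The error is in the safe direction.

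**Working it through.** **1. The plan's own figures.** SAP 4.3.1 claims 90% power for a total-slope difference of 2.9 per year. It also says "approximately 380 patients provide 80% power to detect a smaller treatment effect on eGFR slope at 2 years of 2.55", and gives 1.8 as the observed difference for p<0.02. All use one-sided α = 0.02 (z = 2.054). The implied standard errors agree:
- 2.9/(2.054 + 1.282) = 0.869
- 2.55/(2.054 + 0.842) = 0.881
- 1.8/2.054 = 0.876

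I use 0.88. This is also what the plan's residual error of 5.8 gives when spread over the 11 visits from Week 6 to Week 110 (SD of visit times 0.673 years): 5.8 × √(2/190)/0.673 = 0.884.

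**2. Do the main effects touch the tested parameter?** After imputation every patient has the same visits. With unstructured random effects, the treatment-by-time estimate then equals the plain difference between arms in mean patient slope. Over 241 simulated complete-data fits the largest gap was 2 × 10⁻¹³. A REML fit gave estimate/SE 2.780/0.578 with and without the stratum and baseline main effects. Generalized least-squares checks at given covariance parameters also agreed with AR(1) on the residuals (11 visits, correlation 0.3: 2.374445/0.859884 both ways).

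The identity fails if the AR(1) fallback is applied to the random-effects matrix. In one simulated data set the SE was then 1.07 without and 0.54 with the main effects (time in years); in another fit with time in weeks it was 1.63 and 0.66. The SAP does not say which matrix is meant. The identity is also not exact for the observed-data sensitivity models or the 8.6.3.1 spline.

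**3. Size.** Let R² be the share of variance in patients' observed slopes explained by the strata (assumed). Actual size = 2Φ(−z/√(1 − R²)). For R² = 10% at nominal 5%: 2Φ(−1.96/0.949) = 3.9%. The slope SD implied by 0.88 is 0.88 × √380/2 = 8.58 per year, and the gap between two equal groups is 2 × 8.58 × √R².

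| R² (assumed) | Gap between two equal groups, per year | Size, nominal 5% | Size, nominal 4% |
|---|---|---|---|
| 2% | 2.4 | 4.8% | 3.8% |
| 5% | 3.8 | 4.4% | 3.5% |
| 10% | 5.4 | 3.9% | 3.0% |
| 20% | 7.7 | 2.8% | 2.2% |

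Simulation agrees. With an assumed between-stratum slope SD of 2.5 and within-stratum SD of 4 per year, the mean reported SE was 0.553 against a true SD of 0.492, and size was 0.029. When strata did not predict slope, size was 0.049.

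**4. Power forgone.** Without the terms, power = Φ((d − c·SE)/(SE·√(1 − R²))). With them, power = Φ(d/(SE·√(1 − R²)) − c). For d = 2.9, c = 2.054, SE = 0.88 and R² = 10%: Φ(1.309) = 90.5% against Φ(1.420) = 92.2%.

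The SE of 0.88 is a planning figure. For a random-coefficients analysis on 11 visits, residual error alone gives a patient-slope SD of 5.8/(√11 × 0.673) = 2.6 per year, and the between-patient SD must be added. The documents do not give it. If it is 5, the total is √(5² + 2.6²) = 5.64 and SE = 2 × 5.64/√380 = 0.58.

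| Assumed between-patient slope SD | SE | Points forgone at 2.9/yr, R² 5/10/20% |
|---|---|---|
| 5 | 0.58 | 0.02 / 0.03 / 0.03 |
| 6 | 0.67 | 0.1 / 0.2 / 0.3 |
| 8 | 0.86 | 0.8 / 1.6 / 2.8 |
| plan's implied SE | 0.88 | 0.9 / 1.7 / 3.1 |

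At SE 0.88 the losses are 1.4/2.8/5.5 points for 2.55 per year and 0.6/1.1/1.8 for 3.15. At R² of 1 to 2% the loss is at most 0.6 points for any of the three effects.

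**5. With imputation.** A simulation assumed 20% monotone dropout, four equal strata and blocks of 4, with 30 by-arm imputations and no intermittent gaps (Monte Carlo SE 0.15 points). At R² 5/10/20%, size at nominal 5% was 4.4/3.8/3.2% for the current plan and 4.9/4.7/4.9% with stratum-by-time in the analysis only. It was 5.0/4.8/5.2% with the strata in the imputation model as well.

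**The case against.** The strongest reply is that nothing here is an error. The model is pre-specified and valid, and fixed main effects for strata are ordinary practice. That stands, and it is why the priority is low.

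Three stronger readings are tempting, and the documents do not support them:
- **The SAP contradicts the protocol.** It does not. The protocol calls the analysis stratified but does not define how, and a stratum fixed effect is one admissible implementation.
- **The planned power is undermined.** It is not. SAP 4.3.1 claims "more than 90% power to detect an underlying treatment effect in the rate of change in eGFR over 104 weeks" at 3.15 per year, and the calculation takes no credit for the strata. The current model already gains slightly from the stratified allocation.
- **The strata have no effect whichever covariance structure is used.** This fails if the AR(1) fallback is applied to the random effects, and the SAP leaves that open.

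It can also be said that SAP 8.3 already plans secondary-endpoint analyses within the four randomization strata. Those will show whether slopes differ by stratum, but they are run without imputation and do not enter the confirmatory test. Baseline values do enter the imputation regression, which recovers some information for missing visits only.

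Finally, the gain rests on two quantities that nobody can read from the documents. That also stands: the power benefit may be close to nil, and the upper R² values imply stratum gaps that are large against the 2.9 design effect.

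**Conclusion.** The point holds as a cheap precision improvement, not as the repair of a fault. As far as the handling of strata goes, the slope contrast is unbiased and type I error does not exceed nominal. If strata predict slope, the test is conservative. That result depends only on the assumed R², on allocation balanced within strata and on unstructured random effects (or AR(1) on the residuals). The power cost depends also on the between-patient slope SD, which is not documented, so the range that starts at about zero has to be reported with it. This says nothing about the missing-at-random or on-treatment assumptions, which are separate matters.

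**What to change.** Before unblinding:
1. Add stratum-by-time to the models in SAP 8.6.1 and 8.6.2, and stratum by time-from-baseline and by time-from-change-point in 8.6.3.1.
2. Add the stratification variable to both imputation steps in 6.6.1.1, so that imputed slopes carry the same relationship.
3. Report each arm's slope at observed strata proportions, in line with SAP 8.1, where for LS means "the observed strata proportions will be used instead of assuming equal sizes of strata".
4. Keep the current model as a sensitivity analysis, and state whether the AR(1) fallback refers to the residual or the random-effects matrix.

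If the sponsor prefers to keep the confirmatory model, it should state that the slope contrast is deliberately unadjusted for strata and pre-specify the stratum-by-time model as a sensitivity analysis. A baseline eGFR-by-time term is optional; its gain is not quantified here.

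The cost is SAP wording, 3 degrees of freedom in about 380 patients (4 with the optional term), and slightly more complex analysis and imputation models. No new data are needed.

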### **8.6.2. Rate of Change in eGFR over 110 Weeks Following Initiation of Randomized Therapy**

The rate of change in eGFR over 110 weeks following the initiation of randomized therapy will be analyzed via a mixed model random coefficients analysis.

The response variable is the eGFR measured at on-treatment, post-baseline assessments during the randomized treatment period for each patient. The model will include the following fixed effects:

- Treatment group (2 levels: sparsentan, irbesartan)
- Baseline eGFR
- Time (ie, analysis visit in weeks)
- Treatment group by time interaction
- Randomization stratification variable (4 levels based on Screening eGFR and urine protein excretion)

In addition, random intercept and random slope will be included for each patient.

Under the assumption of MAR, missing data will be imputed using the MI procedure (Ouyang 2017, Rubin 1987). Specific imputation procedures are provided in [Section 6.6.1.1](#).

An unstructured covariance matrix will be assumed; if convergence issues arise, a first order autoregressive structure will be used.

The treatment effect will be the contrast between sparsentan and irbesartan marginal slope estimates. The associated slope estimates, difference in slopes, 95% CI, and 2-sided p-value will be extracted from the model. Slope and the difference in slopes will be annualized for ease of presentation and interpretation.

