### **12.7.2.2. Rate of Change in eGFR Following Initiation of Randomized Therapy**

The rate of change in eGFR 110 weeks (ie, following initiation of randomized therapy) will each be analyzed via a mixed-model random coefficients analysis. Utilizing eGFR data from Day 1 to Week 110, eGFR will be the dependent variable with random patient effects for intercepts and slopes. Fixed effects for randomized treatment, baseline eGFR, time (in weeks), and randomized treatment-by-time interaction will be included. The analysis will be stratified by the randomization strata. An unstructured covariance matrix will be assumed; if convergence issues arise, a first-order, auto-regressive structure will be used. The treatment effect will be the contrast between sparsentan and irbesartan marginal slope estimates. The associated slope estimates, difference in slopes, 95% CI, and two-sided p-value will be extracted from the model. Slope and the difference in slopes will be annualized for ease of presentation and interpretation.

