###### **3.2.1.2. Key Secondary Efficacy Endpoints**

The key secondary efficacy endpoints are listed below:

- The rate of change in estimated glomerular filtration rate (eGFR) over a 52-week (approximately 1-year) period following the initial acute effect of randomized therapy (the initial acute effect of randomized therapy is defined as the first 6 weeks of randomized treatment with study medication; thus, the analysis is from 6 weeks post randomization to 58 weeks post randomization; eGFR chronic slope at 1 year)
- The rate of change in eGFR over a 104-week (approximately 2-year) period following the initial acute effect of randomized therapy (the initial acute effect of randomized therapy is defined as the first 6 weeks of randomized treatment with study medication; thus, the analysis is from 6 weeks post randomization to 110 weeks post randomization; eGFR chronic slope at 2 years)
- The rate of change in eGFR over a 110-week (approximately 2-year) period following the initiation of randomized therapy (thus, the analysis is from Day 1 to 110 weeks post randomization; eGFR total slope at 2 years)

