### 6.5.4. Visit Windows

A visit window method will be applied to determine analysis visits across the study for efficacy and safety endpoints based on laboratory results, including eGFR and quantitative urinalysis (including UP/C). If a patient has multiple assessments (including unscheduled visits) within a visit window, the value closest to the target day for that visit will be selected for analysis. If more than 1 assessment is equidistant to the target day, then latest value will be selected. For efficacy analysis visits on or prior to Week 110, only assessments while the patient is on randomized treatment should be included (see [Section 8.1](#) for definition of on treatment).

The visit windows for the double-blind period shown in [Table 1](#) are defined for endpoints based on laboratory results. Visit windows for the OLE will be defined in a separate SAP.

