**Table 1: Visit Windows (Study Days)**

Analysis Visit	Relative Target Day	Analysis Visit Window (Study Days)	
		eGFR and Safety Labs	Quantitative Urinalysis
Week 2	15	2 – 22	N/A
Week 4	29	23 – 36	2 – 36
Week 6	43	37 – 64	37 – 64
Week 12	85	65 – 127	65 – 127
Week 24	169	128 – 211	128 – 211
Week 36	253	212 – 295	212 – 295
Week 48	337	296 – 372	296 – 372
Week 58	407	373 – 449	373 – 449
Week 70	491	450 – 533	450 – 533
Week 82	575	534 – 617	534 – 617
Week 94	659	618 – 701	618 – 701
Week 106	743	702 – 757	702 – 757
Week 110 	771	758 – 785	758 – 785
Week 114 	799	>785	>785
4-week After EOT 	799  or Last Dose Date + 28 	>785  or >Last Dose Date 	>785  or >Last Dose Date 

eGFR = estimated glomerular filtration rate; EOT = end of treatment.

 For patients who completed the planned randomized treatment period.

 Efficacy endpoints only.

 For patients who discontinued the randomized treatment early.

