### 8.2. Statement of the Null and Alternate Hypotheses

The primary analysis of the primary efficacy endpoint at Week 36 will be ascertained first at primary analysis using the PAS.

The primary analysis of the primary efficacy endpoint will be summarized again at final analysis using the FAS, but will not test hypothesis.

The primary analysis of the primary efficacy endpoint at Week 36 will test the following hypotheses using the PAS at primary analysis:

- H0: Change from baseline in proteinuria (UP/C) is equal between sparsentan and irbesartan
- H1: Change from baseline in proteinuria (UP/C) is different between sparsentan and irbesartan

For non-US countries, the primary analysis of the key secondary endpoint will test the following hypotheses using the subset of patients in the FAS who had completed the Week 58 visit or early

terminated (for those who early terminated, patients need to expect to have visits at least through Week 58):

- H0: Rate of change in eGFR following acute effect over 52 weeks (Week 6 to Week 58) is equal between sparsentan and irbesartan
- H1: Rate of change in eGFR following acute effect over 52 weeks (Week 6 to Week 58) is different between sparsentan and irbesartan

The final analysis of the key secondary endpoints will test the following hypotheses using the FAS:

- H01: Rate of change in eGFR following acute effect over 104 weeks (Week 6 to Week 110) is equal between sparsentan and irbesartan
- H11: Rate of change in eGFR following acute effect over 104 weeks (Week 6 to Week 110) is different between sparsentan and irbesartan
- H02: Change in eGFR from initiation of randomized therapy to 110 weeks is equal between sparsentan and irbesartan
- H12: Change in eGFR from initiation of randomized therapy to 110 weeks is different between sparsentan and irbesartan

The treatment effect refers to the effect of sparsentan minus irbesartan.

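### The 110-week eGFR total slope is defined from Day 1, but SAP 8.6.2 fits it to post-baseline values only, so part or all of any acute difference between the arms drops out of the first US test at the final analysis

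*SAP*

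**What the plan says.** The endpoint and the model do not cover the same period.

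- **Endpoint.** SAP 3.2.1.2 describes the total slope in these words: "thus, the analysis is from Day 1 to 110 weeks post randomization; eGFR total slope at 2 years". The null hypothesis H02 in SAP 8.2 reads "Change in eGFR from initiation of randomized therapy to 110 weeks is equal between sparsentan and irbesartan". SAP 6.5.2 makes the day of first dose Day 1, so both start at the same point.
- **Protocol model.** Protocol 12.7.2.2 says: "Utilizing eGFR data from Day 1 to Week 110, eGFR will be the dependent variable".
- **SAP model.** SAP 8.6.2 says: "The response variable is the eGFR measured at on-treatment, post-baseline assessments during the randomized treatment period for each patient". Baseline eGFR is a fixed-effect covariate, beside treatment, time, treatment by time, and the strata.
- **Supporting rules.** SAP 8.1 gives the on-treatment condition for an assessment as follows: "it occurs after the first dose of study medication and no more than 3 days after the date of last dose of randomized treatment". SAP 6.5.4 adds: "For efficacy analysis visits on or prior to Week 110, only assessments while the patient is on randomized treatment should be included". The first eGFR window in SAP Table 1 is Week 2, study days 2 to 22.
- **Role in testing.** Step 1 of the US procedure in SAP 8.4.2, carried out when the double-blind period is finally analysed, reads: "The key secondary endpoint of eGFR rate of change over 110 weeks following initiation of randomized therapy will be tested at a significance level". That level is 0.05. The Week 6 to 110 chronic slope is Step 2.
- **Declared changes.** SAP 5.4 states consistency with protocol Amendment 5 and does not list this as a change.

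**The concern.** What separates a total slope from a chronic slope is the acute phase, and the value before first dose anchors it. Under SAP 8.6.2 the total-slope response differs from the chronic-slope response of 8.6.1 only by the Week 2 and Week 4 visits. The baseline covariate does not replace the missing anchor: it adjusts the level, while the free treatment main effect absorbs any shift that has already happened by Week 2.

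If sparsentan has the larger acute drop, the estimate moves toward the chronic slope and favours sparsentan. An acute gain would reverse this. Either way, the analysis behind the first US test would not match its stated endpoint, and Steps 1 and 2 would come closer to testing the same thing.

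The sensitivity analyses in SAP 8.6.3 vary imputation, completer status, local laboratory data, post-discontinuation data, immunosuppressant use and the per-protocol set. None returns baseline to the response. The Week 6 knot model in 8.6.3.1 is for the chronic slopes and is also post-baseline only.

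**Working it through.** **Inputs from the documents**
- Visits at Weeks 2, 4, 6, 12, 24, 36, 48, 58, 70, 82, 94, 106 and 110 (SAP Table 1), with baseline at time 0.
- From SAP 4.3.1: 380 patients, residual error 5.8, one-sided alpha 0.02; total-slope differences of 2.9 per year (90% power) and 2.55 (80%); chronic-slope difference 3.15; critical difference 1.8.
- 1:1 allocation (SAP 4.4), so 190 per arm.

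**Assumptions.** Complete visits (SAP 6.6.1.1 imputes missing values) and 52 weeks per year. The acute difference *d* takes one of two shapes: complete by Week 2, or building linearly to Week 6. The first is a boundary case, because titration starts at Week 2 (SAP 4.2.1).

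**Step 1: planning standard error.**
- 2.9/(2.054 + 1.282) = 0.87
- 2.55/(2.054 + 0.842) = 0.88
- 1.8/2.054 = 0.88

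The plan's figures agree with each other.

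**Step 2: what each model keeps of an acute difference.** With complete balanced visits, the random-coefficient slope contrast equals the least-squares slope of the mean difference profile f(t), and a time-constant covariate does not change it:

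slope per year = 52 × Σ(t − t̄)f(t) / Σ(t − t̄)²

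- With time 0 (14 points): t̄ = 46.57, Σ(t − t̄)² = 21171.4.
- Without it (13 points): t̄ = 50.15, Σ(t − t̄)² = 18835.7.

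For f = 1 from Week 2 on:
- with baseline: 52 × 46.57/21171.4 = 0.114
- without: f is constant, so 0.000

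For f = t/6 up to Week 6, then 1:
- with baseline: 52 × 90.48/21171.4 = 0.222
- without: 52 × 47.49/18835.7 = 0.131

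The net Day 1 to Week 110 change would count 52/110 = 0.473 per unit.

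| Acute shape | SAP 8.6.2 | With baseline | Shift per 1 mL/min/1.73 m² |
|---|---|---|---|
| Complete by Week 2 | 0.000 (0% of 0.473) | 0.114 (24%) | 0.114 per year |
| Linear to Week 6 | 0.131 (28%) | 0.222 (47%) | 0.091 per year |

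Against an SE of 0.88 the shift is 10 to 13%. For the exploratory 58-week slope (SAP 8.7.1) the same calculation gives 0.21 to 0.29 per year per unit.

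**Step 3: check with fitted mixed models.** Simulated trials had 190 per arm, the acute change complete by Week 2, assumed intercept SD 20 and slope SD 4, and 10 runs per setting. For acute differences of 0, −2 and −4, the post-baseline estimate minus the baseline-inclusive estimate averaged −0.02, 0.26 and 0.46 (simulation SE 0.02). The formula predicts 0, 0.23 and 0.46.

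**Step 4: what the planning pair might imply.** The documents do not attribute the gap between 2.9 and 3.15 to an acute effect, so these are readings.
- *(a) 2.9 is the net change.* d = (3.15 − 2.9) × 110/52 = 0.53, or 3.15 × 2 − 2.9 × 110/52 = 0.17 if the chronic difference starts only at Week 6. The shift is 0.05 to 0.06 per year, about 6 to 7% of the SE. Take d = 0.53, with the chronic difference set to d × 52/110 so that the Week 110 difference is zero. The nominal two-sided 5% test then rejects in 5.5 to 5.9% of trials, against 5.3 to 5.5% with baseline included (normal approximation).
- *(b) 2.9 is the fitted slope from the protocol model.* Linear build-up: d = 0.25/0.222 = 1.125, SAP slope 3.00, shift 0.10. Complete by Week 2: d = 0.25/0.114 = 2.19, SAP slope 3.15, shift 0.25.

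**The case against.** The strongest reply is that the effect is small and rests on an unknown. Under reading (a) the false-positive rate changes by at most about 0.4 percentage points. The largest shift, 0.25 per year, needs an acute effect finished before titration begins. The range of *d* from 0.17 to 2.19 shows that the planning figures do not fix it. All of this stands, and the dependable result is the rate per unit of acute difference.

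Restoring baseline also recovers only about a quarter of what is lost relative to net change: 0.114/0.473 = 24%, or (0.222 − 0.131)/(0.473 − 0.131) = 27%. The remainder comes from the protocol's own single-slope model and is not an SAP departure. H02 speaks of a change rather than a rate, and a single slope would not test that exactly even with baseline in the response.

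Other analyses do start from baseline: change in eGFR at Week 110 (last in the SAP 8.4.3 order), the Week 6 change and the Week 114 change. They would make an acute loss visible, but they do not replace US Step 1.

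The Amendment 5 text was not available; the protocol supplied is Amendment 6. Its history entry names no change to the slope model but does mention a global consolidation, so a departure from Amendment 5 cannot be confirmed. The conflict between SAP 3.2.1.2 and 8.6.2 does not depend on the protocol version.

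Outside the US, the total slope is tested only after the 2-year chronic slope succeeds (SAP 8.4.1), so the practical concern is mainly US Step 1.

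**Conclusion.** The concern holds. The SAP contradicts its own endpoint definition, and the restriction is deliberate enough (8.1, 6.5.4, 8.6.2) that a programmer following it would drop the time-0 value. The consequence is a shift of 0.09 to 0.11 mL/min/1.73 m² per year for each 1 mL/min/1.73 m² of acute between-arm difference, toward the chronic slope. It is zero if the arms differ linearly from Day 1 with no acute component. This rests on complete visits and the two assumed acute shapes. Neither the sign nor the size of the acute difference is established by the documents, so no bias in a particular direction is claimed. The shift is modest, but it falls on the first US test at the final analysis and should be settled before final unblinding.

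**What to change.** 1. **SAP 8.6.2.** Replace the response sentence with: *The response variable is the double-blind baseline eGFR (Section 6.4.1), assigned to time 0, together with on-treatment post-baseline eGFR through Week 110.* Use the 6.4.1 baseline rather than a strict Day 1 sample, because footnote g of protocol Table 15.1-1 waives the Visit 2 sample and eGFR when the screening sample was taken within the preceding 14 days.
2. **SAP 8.1 and 6.5.4/Table 1.** Add: *For the eGFR total-slope analyses, the double-blind baseline is included as a response at time 0 and is exempt from the on-treatment restriction.*
3. **SAP 8.7.1.** Make the same change through Week 58, for consistency with the exploratory endpoint in 3.2.2.
4. **Covariate.** State that baseline eGFR also remains a covariate, as in the protocol model.

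A two-slope sensitivity analysis of total slope, with a Week 6 knot and baseline in the response, would be a useful option but is not needed for the fix.

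The cost is short wording edits and minor reprogramming. No new data are needed, since the same baseline is already the covariate. Precision is not lost: by generalised least squares with 190 per arm and residual SD 5.8, the SE is 0.878 with baseline and 0.881 without (assumed slope SD 8.3 per year, chosen to match the planning SE), or 0.555 and 0.560 (assumed slope SD 5). If sparsentan does have the larger acute drop, its estimate will be slightly less favourable.
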